## 5.5 Dose Modifications

All toxicities should be graded according to the NCI Common Terminology Criteria for Adverse Events (CTCAE) version 4.0.

All appropriate treatment areas should have access to a copy of the CTCAE version 4.0. A copy of the CTCAE version 4.0 can be downloaded from the CTEP web site (<http://ctep.cancer.gov>).

Rev. 11/13  
9/14

**NOTE:** Per Addendum #7, the dose modification plan for Arms A and D (ipilimumab 10 mg/kg) has been modified to become stricter due to a higher incidence of severe toxicities observed on Arms A and D than seen in Arms C and F. Arms C and F dose modification guidelines continue to be the same, with minor changes.

Rev. 2/12, 11/13  
9/14

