#### 9.1 Previous Study Design

Initially this study was designed to compare the high-dose (10mg/kg) ipilimumab (Ipi) vs. HDI. The study was activated on May 25, 2011. Subsequently the importance of the low-dose Ipi (3mg/kg) in this patient population was discussed based on the results of the MDX010-20 trial and the FDA approval of ipilimumab at 3 mg/kg in the treatment of metastatic melanoma, leading to the addition of the 3 mg/kg arm to this trial as of January 2012. Since then patients are randomized to three treatment arms: High dose interferon-alfa (HDI), high dose ipilimumab (HIP) and low dose ipilimumab (LIP).

With the addition of low dose ipilimumab (LIP) arm, a two-step hierarchical approach was adopted. In the first step, the high-dose Ipi was to be compared with HDI. If the high-dose Ipi is significantly better than HDI, then the low-dose Ipi was to be compared with HDI as a second step. However, the order of the comparison has been revised to the low-dose Ipi vs. HDI first then to the high-dose Ipi vs. HDI in February 2015. This revision was made since the low-dose Ipi has become the standard of care in the treatment of metastatic melanoma. Since no formal interim analysis had been conducted prior to this revision, this change did not affect the overall type I error rate of the study design.

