## 9.2 Primary Objective

This is a randomized phase III study of high-dose Ipi (HIP) vs. low-dose Ipi (LIP) vs. HDI in patients with resected high-risk melanoma. Approximately 1500 patients will be randomized equally among the three treatment arms, stratified by the AJCC stage (IIIB, IIIC, M1a, M1b). The stratified randomization will be based on the permuted block method.

Rev. 9/14

This study has a two-step hierarchical approach. In the first step, the low-dose Ipi will be compared with HDI. If the low-dose Ipi is significantly better than HDI, then the high-dose Ipi will be compared with HDI as a second step. When comparing the two investigational treatment groups, the primary comparison will be an intent to treat (ITT-defining groups by assigned treatment) analysis of recurrence free survival (RFS; **First Co-primary Endpoint**) and overall survival (OS; **Second Co-primary Endpoint**) in all patients compared to HDI. Both of these endpoints will be used as co-primary endpoints in the sense that the study will be considered a positive study if it meets either one of these 2 endpoints (see Section [1.7.1](#)). That is, in the first step of comparing the low-dose Ipi vs. HDI, it will be a positive study if the low-dose Ipi has better RFS or OS outcome. Then the comparison will proceed to the second step where the high-dose Ipi will be compared to HDI. In each comparison, patients concurrently randomized to the two arms being compared will be included in the analysis. . If high-dose Ipi leads to a better RFS or OS outcome than the HDI, it will be considered as a positive study with respect to the second comparison.

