#### 9.8.2 Toxicity data analysis

Adverse events (AE) data will be summarized based on the data collected in ECOG CRFs as well as the data reported via CTEP-AERS. Individual toxicity type AE and categorized AE data (by autoimmune disorders, endocrine, GI, liver, nervous system, pancreas, psychiatric disorders, skin, thromboembolic disorders) will be summarized by grade and treatment arm. The percentages of patients experiencing the worst degree toxicities (highest grade event per AE type per patient) will be evaluated and the distribution of the worst degree toxicities will be compared among the treatment arms. The proportion of patients with worst degree toxicities with 3 or higher will be summarized and compared among the treatment arms. Chi-square test will be used for AE comparisons. For the AE data, any patient who received treatment will be included.

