#### 9.8.3 Other secondary analyses

The QOL study is open to patients enrolling from CCOPs. FACT-G, FACIT-D and FACT-BRM forms will be collected every 3 months while on treatment and every 6 months off-treatment for one year.

The main comparison for all forms will be the change in QOL measurements between the baseline and 3 month time point by treatments (high-dose Ipi vs, HDI or low-dose Ipi vs. HDI). Descriptive statistics on QOL measurements will be provided. Two-sample t-test

will be used for each comparison and two-sided p-values will be reported. ITT analysis on all cases with QOL data will be conducted.

At the final analysis, subgroup analyses of the treatment effects on RFS and OS will be conducted. Subgroups by age, sex, ECOG PS, AJCC stage (IIIB, IIIC, M1a, M1b), ulceration status of the primary, type of lymph node involvement (microscopic / macroscopic), extent of lymph node involvement (1 vs 2-3 vs  $\geq 4$  positive LN) will be considered in the ITT patient population. This analysis will be summarized using the forest plots with HRs and 95% CIs.

In the event of missing data, it will be assumed that the data will be missing at random and no imputation will be performed.

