### 9.10.1 Arm A Toxicity Monitoring

Grade 5 AE data reported via CTEP-AERS system has been reviewed by ECOG-ACRIN DSMC. Based on the data as of 9/23/13, there had been 8 grade 5 AEs potentially treatment-related in arm A. At that time, there were 405 patients who were treated with 10mg/kg Ipi dose. While AE data was being reviewed by ECOG-ACRIN DSMC, accrual to arm A was suspended and treatment for the patients randomized to arm A was held. Upon reopening the arm A for accrual and grade 5 AE data will be reviewed carefully. When there is a new grade 5 AE event in arm A, a study statistician will be alerted. The rate of grade 5 potentially treatment-related AE will be estimated by dividing the total number of cases with grade 5 potentially treatment-related AEs by (total accrual in arm A – cases never started therapy). If this rate is greater than or equal to 2.5%, ECOG-ACRIN DSMC will be notified and this matter will be discussed. If this rate is reached, it will require suspension of accrual to arm A while the review is conducted.

For a cutoff rate of 2.5%, the rule would be 11 events in 440 or fewer treated patients, 12 events in 480 or fewer patients, or 13 in > 480 (assuming < 520 entered). Given that we already have observed 8 potentially treatment-related grade 5 AE events in 405 patients, the conditional power for the proposed rule can be estimated by: the probability of 3 or more (to reach 11) in 35, plus the probability of 4 or more in 75 given < 3 in the first 35, plus the probability of 5 or more in 95 given < 3 in the first 35 and < 4 in the first 75. Then the conditional power is 3.7% for a true grade 5 AE rate of 1.5%, 8.5% for a true grade 5 AE rate of 2.0%, 15.3% for a true rate of 2.5%, 23.6% for a true rate of 3.0%, 32.9% for a true rate of 3.5%, 42.5% for a true rate of 4.0%, and 60.4% for a true rate of 5.0%. Conditional power is not particularly high given that we have already observed 8 cases with grade 5 AEs out of 405 treated patients. However this toxicity monitoring rule will provide some guidance for a formal review by ECOG-ACRIN DSMC.

Rev. 9/14,  
9/14

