### **Power Justification**

The target accrual for E1609, which was activated in May 2011, is 1600 (600 HDI, 500 HIP, 500 LIP), which will be completed by August 2014. Thus, by 2015, we will have at least 1 year of follow-up data for each patient in the trial for analysis and validation of potential biomarkers and the development of prediction models for RFS and OS of the patients in each treatment arm.

We currently estimate that biospecimens are available for testing from approximately 80% of subjects enrolled on E1609. We expect that these numbers will improve as we continue to follow up with participating sites on biospecimen submission.

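### AE and QOL comparisons with the low-dose arm lack the concurrency limit applied to RFS and OS, so they include patients enrolled before that arm opened

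*Combined protocol and SAP*

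**What the plan says.** Section 9.1 gives the timeline. For high dose (10 mg/kg) and HDI, "The study was activated on May 25, 2011". The low-dose arm followed later, with new results and the FDA approval "leading to the addition of the 3 mg/kg arm to this trial as of January 2012".

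For RFS and OS the plan deals with this. Section 9.2 states: "In each comparison, patients concurrently randomized to the two arms being compared will be included in the analysis". Section 9.3 recognizes that low dose needs a concurrent HDI control, and 9.5 uses only HDI patients enrolled after low dose was added.

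For safety, 9.7.1 defines the population as everyone who was dosed. Section 9.8.2 compares worst-grade AEs among the arms by chi-square and adds: "For the AE data, any patient who received treatment will be included". For QOL, 9.8.3 plans two pairwise t-tests, each ipilimumab dose against HDI, and says: "ITT analysis on all cases with QOL data will be conducted". None of these three sections limits or stratifies by enrolment period.

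On the 10 mg/kg arm, 5.5 says that under Addendum #7 (margin note 11/13) the dose-modification plan "has been modified to become stricter due to a higher incidence of severe toxicities observed on Arms A and D", while the 3 mg/kg guidelines stayed the same apart from minor changes. Section 9.10.1 gives the position on 23 September 2013: "At that time, there were 405 patients who were treated with 10mg/kg Ipi dose".

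**The concern.** A patient randomized between May and December 2011 could be assigned high dose or HDI but not low dose. When such patients enter a comparison with low dose, that part of the comparison is not randomized: it sets an earlier cohort against a later one. Any change over those months in case mix, monitoring, AE reporting or investigator experience with immune-related events then appears as a treatment difference.

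The plan guards against this for its co-primary endpoints but not for safety or QOL. The gap matters because Section 1.6 gives a possible difference in toxicity between 3 and 10 mg/kg as a reason for adding the low-dose arm. The AE contrasts involving low dose are the ones exposed. High dose versus HDI is not affected at the early end, because those patients were randomized side by side.

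**Working it through.** **The plan's own figure.** The only power statement for these analyses is in 9.7.2: 150 per arm, standardized difference 0.4, one-sided 0.025, at least 80%. With power = Φ(0.4·√(n₁n₂/(n₁+n₂)) − 1.960), 150 versus 150 gives 0.4·√75 − 1.960 = 1.504, or 93.4%. The statement holds; 80% needs 99 per arm.

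**Early non-concurrent patients.** Appendix XIX.8 gives accrual targets of 600 HDI, 500 high dose and 500 low dose. Section 9.3 requires 500 HDI patients from the time low dose opens.
- HDI before low dose: 600 − 500 = 100, or 100/600 = 16.7%.
- High dose before low dose, assuming 1:1 early randomization: about 100, or 100/500 = 20%.
- Cross-check from the planned rate of 38 per month (9.3) over about 7.2 to 8.2 months: 38 × 7.2/2 = 137 to 38 × 8.2/2 = 156 per arm. This is probably an upper range, since it applies the full planned rate from the first day.
- With an assumed range of 50 to 150 per arm, the shares are 9–23% of HDI (50/550 to 150/650) and 10–30% of high dose.

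**Late non-concurrent patients.** Section 9.3 stops high dose at 500 while low dose and HDI continue, and 9.10.1 records a suspension of Arm A in 2013. If 100 high-dose patients came before low dose, about 400 remain alongside 500 low-dose and 500 later HDI patients. With equal randomization while all three arms were open, about 500 − 400 = 100 in each of those arms had no concurrent high-dose patient.

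**What drift would do.** Let w be the early share and d the difference in AE rate between the early and later periods. The bias is w·d. The table takes w = 1/6 for HDI (500 versus 600) and w = 1/5 for high dose (500 versus 500), and gives the true size of a two-sided 5% chi-square test when there is no difference among concurrent patients. The drift values are assumptions. The base rates are illustrative, close to the 25.2% and 46% in 9.7.1.

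| Drift d | Bias, low dose vs HDI | Bias, low vs high dose | Size at 25% base (HDI; high dose) | Size at 46% base (HDI; high dose) |
|---|---|---|---|---|
| 5 points | 0.8 | 1.0 | 6.1%; 6.5% | 5.9%; 6.2% |
| 10 points | 1.7 | 2.0 | 9.6%; 11.1% | 8.5%; 9.7% |
| 15 points | 2.5 | 3.0 | 15.4%; 18.9% | 13.1%; 15.8% |

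These figures cover the early end only.

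**Precision lost by restricting.**
- AE, low dose versus HDI, 500 versus 600 becoming 500 versus 500: √[(1/500 + 1/500)/(1/500 + 1/600)] = 1.044, so the standard error rises 4.4%.
- AE, low versus high dose, 500 versus 500 becoming about 400 versus 400: √(500/400) = 1.118, a rise of 11.8%.
- QOL, low dose versus HDI: if the early share is the same among QOL patients, HDI falls to 150 × 500/600 = 125. Power is Φ(0.4·√68.18 − 1.960) = 91.0%. In a harsher case of 150 versus 100 it is Φ(0.4·√60 − 1.960) = 87.3%.

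**Arm A and Addendum #7.** Of about 500 to 520 patients (520 is the ceiling assumed in 9.10.1), 405 had started by 23 September 2013: 405/520 = 78% to 405/500 = 81%. This counts patients who had started treatment, not patients treated wholly under the earlier criteria.

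**The case against.** The strongest reply is that 9.8.2 only defines a treated population and does not address enrolment period. Section 9.8.1 uses similar all-cases wording for RFS and OS, where 9.2 is still understood to apply. On that reading the safety and QOL sections merely lack a cross-reference. This does not settle the matter. Section 9.2 sits under the primary objective and speaks of RFS and OS, whereas 9.8.2 gives its own inclusion rule with no period limit. An analyst who follows 9.8.2 as written will include the early patients. If the authors intended otherwise, the text still has to say so.

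The objections on size have more force. The 100-patient figure comes from appendix targets, and 9.3 says only that HDI will slightly exceed 500. The documents report no drift. At 5 to 10 points of drift the bias is 0.8 to 2.0 points, against an 18.4-point gap in grade 3–4 irAEs between 3 and 10 mg/kg in the earlier dose-ranging study (7.0% and 25.4%, Table 3). The QOL analysis is called exploratory, and no decision rule rests on the AE or QOL tests. These points stand and limit the priority.

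A reader might also infer a three-arm QOL comparison, or a QOL contrast between the two doses. The documents plan neither: QOL is pairwise against HDI, so early enrolment affects only low dose versus HDI.

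**Conclusion.** The gap is real and worth closing, at the level of secondary analyses. As written, low dose versus HDI (AE and QOL) and low dose versus high dose (AE only) include patients enrolled before low dose existed: about 17% of HDI and about 20% of high dose. These shares rest on the 600/500/500 targets and, for high dose, on 1:1 early randomization. Contrasts involving high dose can also lose concurrency late in accrual. The size of any bias depends on drift that the documents do not report.

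Two stronger readings are tempting. One is that a dose effect on toxicity cannot be separated from changes over time. The targets do not support this: about 80% or more of each arm is concurrent with its comparator, and a date filter isolates those patients. The other is that pooling Arm A across Addendum #7 makes the comparison one between different periods. It does not. Pooling mixes two versions of the delay and discontinuation criteria within one arm, which affects what a single Arm A rate describes. That is a separate, descriptive point.

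**What to change.** In 9.8.2 and 9.8.3, state that every pairwise AE and QOL test uses patients concurrently randomized to the two arms being compared, as in 9.2, at both ends of accrual. A start-date filter alone is not enough, because it leaves in low-dose and HDI patients enrolled while high dose was suspended or closed. Keep the all-treated tables as descriptive within-arm summaries.

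As a separate descriptive table, show Arm A AEs before and after the Addendum #7 change. Therapy lasts about 60 weeks (5.7.1) and Arm A treatment was held during the 2013 review, so some patients span both versions of the criteria. The table should identify them rather than allocate them by first-dose date alone.

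The cost is SAP wording and a randomization-date filter, with fewer patients per contrast. On the target numbers the AE standard error rises about 4% for low dose versus HDI and about 12% for low versus high dose. QOL power for low dose versus HDI is about 87–91%, still above the stated 80%.

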#### 9.8.3 Other secondary analyses

The QOL study is open to patients enrolling from CCOPs. FACT-G, FACIT-D and FACT-BRM forms will be collected every 3 months while on treatment and every 6 months off-treatment for one year.

The main comparison for all forms will be the change in QOL measurements between the baseline and 3 month time point by treatments (high-dose Ipi vs, HDI or low-dose Ipi vs. HDI). Descriptive statistics on QOL measurements will be provided. Two-sample t-test

will be used for each comparison and two-sided p-values will be reported. ITT analysis on all cases with QOL data will be conducted.

At the final analysis, subgroup analyses of the treatment effects on RFS and OS will be conducted. Subgroups by age, sex, ECOG PS, AJCC stage (IIIB, IIIC, M1a, M1b), ulceration status of the primary, type of lymph node involvement (microscopic / macroscopic), extent of lymph node involvement (1 vs 2-3 vs  $\geq 4$  positive LN) will be considered in the ITT patient population. This analysis will be summarized using the forest plots with HRs and 95% CIs.

In the event of missing data, it will be assumed that the data will be missing at random and no imputation will be performed.

### 9.9 Gender and Ethnicity

Based on previous data from E4697 and E1694, the anticipated accrual in subgroups defined by gender and race is:

Ethnic Category	Gender		
	Females	Males	Total
Hispanic or Latino	2	6	8
Not Hispanic or Latino	567	925	1492
Ethnic Category: Total of all subjects	569	931	1,500

Racial Category			
American Indian or Alaskan Native	0	0	0
Asian	0	2	2
Black or African American	3	3	6
Native Hawaiian or other Pacific Islander	0	0	0
White	566	926	1492
Racial Category: Total of all subjects	569	931	1,500

The accrual targets in individual cells are not large enough for definitive treatment comparisons to be made within these subgroups. Therefore, overall accrual to the study will not be extended to meet individual subgroup accrual targets.

## 9.10 Study Monitoring

Rev. 11/13  
Rev. 11/13

This study will be monitored by the ECOG-ACRIN Data Safety Monitoring Committee (DSMC). The DSMC meets twice each year. For each meeting, all monitored studies are reviewed for safety and progress toward completion. When appropriate, the DSMC will also review interim analyses of outcome data. Copies of the toxicity reports prepared for the DSMC meetings are included in the study reports prepared for the ECOG-ACRIN group meeting (except that for double blind studies, the DSMC may review unblinded toxicity data, while only pooled or blinded data will be made public). These group meeting reports are made available to the local investigators, who may provide them to their IRBs. Only the study statistician and the DSMC members will have access to interim analyses of outcome data. Prior to completion of this study, any use of outcome data will require approval of the DSMC. Any DSMC recommendations for changes to this study will be circulated to the local investigators in the form of addenda to this protocol document. A complete copy of the ECOG-ACRIN DSMC Policy can be obtained from the Coordinating Center.

Rev. 11/13

### 9.10.1 Arm A Toxicity Monitoring

Grade 5 AE data reported via CTEP-AERS system has been reviewed by ECOG-ACRIN DSMC. Based on the data as of 9/23/13, there had been 8 grade 5 AEs potentially treatment-related in arm A. At that time, there were 405 patients who were treated with 10mg/kg Ipi dose. While AE data was being reviewed by ECOG-ACRIN DSMC, accrual to arm A was suspended and treatment for the patients randomized to arm A was held. Upon reopening the arm A for accrual and grade 5 AE data will be reviewed carefully. When there is a new grade 5 AE event in arm A, a study statistician will be alerted. The rate of grade 5 potentially treatment-related AE will be estimated by dividing the total number of cases with grade 5 potentially treatment-related AEs by (total accrual in arm A – cases never started therapy). If this rate is greater than or equal to 2.5%, ECOG-ACRIN DSMC will be notified and this matter will be discussed. If this rate is reached, it will require suspension of accrual to arm A while the review is conducted.

For a cutoff rate of 2.5%, the rule would be 11 events in 440 or fewer treated patients, 12 events in 480 or fewer patients, or 13 in > 480 (assuming < 520 entered). Given that we already have observed 8 potentially treatment-related grade 5 AE events in 405 patients, the conditional power for the proposed rule can be estimated by: the probability of 3 or more (to reach 11) in 35, plus the probability of 4 or more in 75 given < 3 in the first 35, plus the probability of 5 or more in 95 given < 3 in the first 35 and < 4 in the first 75. Then the conditional power is 3.7% for a true grade 5 AE rate of 1.5%, 8.5% for a true grade 5 AE rate of 2.0%, 15.3% for a true rate of 2.5%, 23.6% for a true rate of 3.0%, 32.9% for a true rate of 3.5%, 42.5% for a true rate of 4.0%, and 60.4% for a true rate of 5.0%. Conditional power is not particularly high given that we have already observed 8 cases with grade 5 AEs out of 405 treated patients. However this toxicity monitoring rule will provide some guidance for a formal review by ECOG-ACRIN DSMC.

Rev. 9/14,  
9/14

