## 9.3 Sample Size and Accrual

Approximately 1500 patients will be enrolled over 3.3 years. Accrual rate is expected to be 38 per month. Note that the low-dose Ipi arm will be added in January 2012 and the low-dose Ipi arm will need a concurrent HDI arm as control group. Each group has a sample size of about 500 cases. After the low-dose Ipi is added, patients will be still randomized equally to three treatment arms. Accrual to high-dose Ipi arm will be suspended when it reaches 500 cases. For the other two arms (low-dose Ipi and HDI), accrual will continue until each arm has 500 cases since the time of adding the low-dose Ipi arm. This will lead to a slightly larger sample size (> 500) for the HDI arm. However, it is expected that the overall accrual period necessary for completion of the 3mg/kg dose arm and concurrent HDI accrual will not be more than several months due to this adjustment. Every effort will be made to shorten the accrual duration with active intergroup participations. With additional follow up time, a total duration of study is expected to be less than 6 years. The primary comparisons of RFS and OS will be performed using the log-rank test stratified on AJCC stage.

Rev. 9/14

Per amendment #10, approximately 45 adolescent patients (ages 12-17) will be enrolled. If accrual to the adult population reaches its goal before 45 adolescent patients enroll to this study, the study will remain open only to the adolescent population until 2016. If the adolescent population reaches its accrual goal of 45 before the adult population reaches its accrual goal, adolescent accrual will be closed. With the data from a small group (45 or less) of adolescent population, analysis will be mostly descriptive and exploratory.

Rev. 3/15

As of August 15, 2014, adult accrual to Arms A, B, and C has completed. Adolescent patients (ages 12 -17) will be randomized to study arms D, E, and F.

Rev. 9/14

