### 9.11 Adolescent Patients

As of amendment #10 activation, E1609 age eligibility criteria will be expanded to allow adolescent patients ages 12–17 years old. This is based on preliminary safety and tolerability data reported in study NCI 7458. UP to 45 patients will be randomized into the 3 study arms as follows: up to 15 patients on Arm D (ipilimumab 10 mg/kg), up to 15 patients on Arm E (HDI) and up to 15 patients on Arm F (ipilimumab 3 mg/kg). This patient sample size of 45 will be in addition to the approximately 1500 adult patients planned to be enrolled on this trial. The primary study objective for the adolescent patient population is safety. This includes the frequency of study treatment related adverse events with a focus on the frequency and severity of ipilimumab induced immune mediated adverse reactions in adolescent patients with resected high risk melanoma (Stage IIIB, IIIC, M1a, M1b) as the primary endpoint in this study population. Further, the plans for the adult population study analysis will not be impacted by the accrual in the adolescent population part of the study.

Rev. 3/15 **10.**

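### The protocol's only numerical Grade 5 limit (section 9.10.1) can suspend accrual to Arm A alone, although the same 10 mg/kg regimen could still enrol adolescents on Arm D once adult accrual was complete

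*Combined protocol and SAP*

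**What the plan says.** Section 9.10.1 was written when Arm A was about to reopen after a safety suspension. It records that by 23 September 2013 "there had been 8 grade 5 AEs potentially treatment-related in arm A" and that "there were 405 patients who were treated with 10mg/kg Ipi dose". It then sets out a rule in four parts:

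- **Alert:** "When there is a new grade 5 AE event in arm A, a study statistician will be alerted".
- **Rate:** potentially treatment-related Grade 5 cases, divided by "total accrual in arm A" less patients who never started therapy.
- **Notification:** at 2.5% or more the DSMC is told and discusses the matter.
- **Suspension:** "If this rate is reached, it will require suspension of accrual to arm A while the review is conducted".

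The Schema and sections 4, 5.2 and 9.3 state that adult accrual to Arms A, B and C was complete as of 15 August 2014. Adolescents are randomized to Arms D, E or F, which follow the regimens of A, B and C respectively. Section 9.3 adds that, if adults finish first, "the study will remain open only to the adolescent population until 2016". Section 9.11 allows up to 15 adolescents on Arm D at 10 mg/kg and makes safety their primary objective, but gives no Grade 5 limit and no suspension rule. Other sections were revised to cover both arms. Section 5.5, for example, says that "the dose modification plan for Arms A and D (ipilimumab 10 mg/kg) has been modified to become stricter".

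**The concern.** A suspension rule protects patients who have not yet been enrolled. Once adult accrual was complete, the patients who could still be enrolled at 10 mg/kg were the adolescents on Arm D, and the rule's suspension does not name that arm. Neither do its alert and its denominator. Dosing, dose-modification and expedited-reporting text was extended to Arm D, but section 9.10.1 was not, and no reason is given.

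At stake is whether minors could go on being enrolled at a dose that had just reached the protocol's own fatal-toxicity limit, with any pause left to discretion where the rule makes it mandatory for Arm A. Section 9.10.1 shows why an automatic pause matters: in 2013, Arm A accrual was suspended and treatment held during review at 8/405 = 1.98%, which is below the limit later adopted.

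**Working it through.** **1. The plan's own figures.** Inputs from section 9.10.1 are 8 events in 405 treated, with limits of 11 events in up to 440 patients, 12 in up to 480, and 13 above 480 (fewer than 520 entered).

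- The limits agree with 2.5%: 11/440 = 12/480 = 13/520 = 2.5%.
- Further patients: 440 − 405 = 35, 480 − 405 = 75, 500 − 405 = 95. Further events needed: 11 − 8 = 3, 12 − 8 = 4, 13 − 8 = 5.
- With X(n) the number of new events in n further patients, the probability of reaching the limit is P[X(35) ≥ 3] + P[X(35) < 3, X(75) ≥ 4] + P[X(35) < 3, X(75) < 4, X(95) ≥ 5], by exact binomial enumeration.

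| True rate | Stated | Recomputed |
|---|---|---|
| 1.5% | 3.7% | 3.72% |
| 2.0% | 8.5% | 8.48% |
| 2.5% | 15.3% | 15.27% |
| 3.0% | 23.6% | 23.63% |
| 3.5% | 32.9% | 32.93% |
| 4.0% | 42.5% | 42.51% |
| 5.0% | 60.4% | 60.45% |

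The arithmetic of the rule is correct. The question is which arms it covers.

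**2. What each part of the rule does after adult accrual is complete.**

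| Part | Arm named | Effect once only D, E and F enrol |
|---|---|---|
| Alert to statistician | A | Still works for late Arm A events; not set off by Arm D |
| Rate | A (denominator) | Still computable; Arm D not included |
| DSMC notification and discussion | None; follows from the rate | Still mandatory |
| Accrual suspension | A | No open arm to act on |

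The sentence defining the numerator names no arm, but the alert and the denominator do, so Arm A is the only consistent reading.

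**3. Could the Arm A rate still cross during adolescent accrual?** Maintenance doses run to week 60 (section 5.2.1), and adverse events are assessed until 70 days after the last dose (section 7.2). For a patient entered on 15 August 2014, 60 × 7 = 420 days leads to about October 2015, and 70 more days to about December 2015. Section 9.3 keeps adolescent accrual open until 2016, so the periods can overlap. These are latest dates. Section 9.3 closes the high-dose arm at 500 while the other two arms continue, so Arm A may have closed earlier. At 500 treated (an assumption), 12/500 = 2.40% does not reach the limit and 13/500 = 2.60% does.

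**4. Size on Arm D.** If all 15 patients are treated, one death is 1/15 = 6.7%. The chance of at least one, 1 − (1 − p)^15, is 20% at p = 1.5%, 32% at 2.5% and 54% at 5%.

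**5. Would pooling A and D help?** With 500 + 15 = 515 treated, the limit stays at 13 (13/515 = 2.52%; 12/515 = 2.33%). One Arm D death moves the pooled rate by 1/515, or about 0.2 percentage points. Pooling therefore barely registers an adolescent signal.

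**The case against.** The strongest reply is that section 9.10.1 was limited to Arm A by design. Its title names Arm A, it was written for that arm's reopening, it is calibrated to 8 in 405 plus 95 more patients, and it describes itself as guidance for a formal DSMC review. Adolescents have their own section, and their data are to be analysed mainly descriptively. The joint wording on severe toxicity in section 5.5 is weak evidence of one safety population, because that change is attributed to Addendum #7 (Rev. 11/13), before Arm D was added (Rev. 9/14). All of this is fair, and it is a reason to leave the Arm A rate alone. It does not explain why the pause should not reach an open arm on the same regimen.

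Three stronger readings are tempting, and the documents do not support them:

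- **That the limit became inert.** DSMC notification and discussion do not depend on open accrual, and nothing in the text prevents the DSMC from pausing Arm D.
- **That an Arm D death goes unmonitored.** All deaths require routine and expedited reporting (5.3.6). The DMC reviews toxicity in all treated patients and monitors it by dose (9.7.1), the case-selection text of Appendix XIX places Arm D in the high-dose group, and the DSMC meets twice a year (9.10). None of these sections gives a numerical Grade 5 limit, so they narrow the gap without closing it.
- **That 8.5% or 23.6% is the chance of crossing after Arm A closed.** Those figures cover the whole path from 405 to 500 treated, during which Arm A was enrolling and its suspension could act. The documents give no Grade 5 count after September 2013, so the later chance cannot be computed.

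**Conclusion.** The point holds in a limited form. As written, the only numerical Grade 5 limit in the protocol had no open arm to suspend once adult accrual was complete, and a Grade 5 event on Arm D did not set off its alert. Notification of the DSMC, expedited reporting and routine review remained in place.

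The exposure is at most 15 adolescents, for the time between the closing of Arm A and the end of adolescent accrual. This rests on the stated accrual dates, on 15 August 2014 being the latest rather than the actual closing date of Arm A, and on late Arm A events being possible during maintenance and follow-up. It does not assume that the limit was ever reached. It is worth correcting because section 9.11 makes safety the adolescents' primary objective and the correction is small.

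**What to change.** Reconcile sections 9.3, 9.10.1 and 9.11. In 9.10.1, state that:

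- reaching 2.5% on Arm A requires accrual to be suspended, during DSMC review, on any 10 mg/kg arm then open, including Arm D; and
- each potentially treatment-related Grade 5 event on Arm D alerts the study statistician and the DSMC.

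Leave the Arm A rate and its printed limits unchanged. Whether to pool Arms A and D is for the sponsor and the DSMC.

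The cost is one or two sentences and no new data, since all deaths are already reported. The downside is that adolescent accrual could pause on adult data. The current text describes events in 2018, so adolescent accrual may already have ended. In that case, record how the rule was applied to Arm D while it was open, including any Grade 5 event on that arm and any crossing of 2.5% on Arm A.
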